15.2 Data Privacy

Subjects will be identified on CRFs or similar documents (e.g. questionnaires) by a unique anonymized subject identification code. Completed CRFs or similar documents are confidential documents and will only be available to the Sponsor and their representatives, the investigator, the study statistician, and if requested to the Ethics Committee and national regulatory authorities.

The investigator and site staff will not include the name of any subject in any CRF or other forms, electronic files, publication, or submission to a regulatory authority; will not otherwise disclose the identity of any subject; and, in any CRF, will refer to each subject by his/her identification code.

16 Incident reporting

16.1 Incident Reporting

This investigation is performed using CE marked devices thus requiring active recording of incidents of serious and non-serious degree, and immediate reporting of serious incidents as described under the current version of the Medical Device Regulation, 2017/745. Definition of Incident:

"Any malfunction or deterioration in the characteristics or performance of a device made available on the market, including use-error due to ergonomic features, any inadequacy in the information supplied by the manufacturer as well as any undesirable side-effect.

A 'serious incident' means any incident that directly or indirectly led, might have led or might lead to any of the following:

- the death of a patient, user or other person,
- the temporary or permanent serious deterioration of the patient's, user's or other person's state of health,
- a serious public health threat;

16.2 Reporting process

The investigator shall report all serious incidents without undue delay to the sponsor, EC and as applicable to the National Competent Authority (NCA):

Name of contact person of the sponsor: [REDACTED]

Fax: [REDACTED]

E-mail: [REDACTED]

The Sponsor shall assess all reported incidents with the investigator, co-ordinate appropriate actions, if required, and provide the NCA with a final report.

Appropriate treatment of the subject shall be initiated. Study follow up shall continue when appropriate and ethical.

The investigator shall report all incidents to his/her EC using the applicable report form as per national requirement.

17 Vulnerable population

As some individuals in the elderly population may have special needs to help them understand what is involved in the process of study participation, before they can even consider to provide consent to their participation, special considerations are needed to ensure communication of the study processes, additional risks and benefits to them over routine care is understood. Communications should be tailored to help them understand through verbal and written communication with opportunities to ask questions each step of the way. The patient should understand that their participation is entirely optional and voluntary and that in no way affects the routine care they would normally receive if they do not participate.

As a well-established therapy for hearing impairment, cochlear implant treatment is approved as a safe and effective therapy in the long term for patients of all ages. Participation in the observational study presents no additional risks to the patient over routine clinical treatment as only market approved devices and indications are considered.

As elderly patients may be more susceptible to changes in health status, should the individual's general health decline during the course of the study, preventing their comfortable participation in the study processes, the clinician should react in a timely manner to remove the subject from the study formally by completion of the end of study form.

18 Suspension or premature termination

The Sponsor will withdraw from sponsorship of the observational study if,

- 1.) major non-adherence to the study protocol is occurring
- 2.) it is anticipated that the subject recruitment will not be adequate to meet the objectives of the observational study

Should the sponsor withdraw from sponsorship of the observational study, the sponsor will continue sponsorship for the subjects already recruited into the study.

An ongoing observational study can be discontinued in case of:

- 1) Device failure
- 2) Subject's death
- 3) Investigator's decision
- 4) Subject's decision

19 Publication Policy

It is planned to generate at least two joint publications by the clinical investigator(s), with support from the sponsor using collective data. Depending from the interim analysis outcomes a potential preliminary publication for completion of 1 year evaluation by a subgroup of the study cohort will be written and submitted.

The responsibility for writing the publications will be agreed with the co-investigator group. Authorship will be based on contribution of complete datasets and contribution to paper preparation according to the rules of the journal(s) chosen for publication. Publications are requested to be reviewed by the sponsor at least 30 days in advance to submission for publication. This study does not include data collection related to patency issues.

Investigators are able to publish their local data separately, ensuring statistical validity of data analysis and any conclusions made. The sponsor kindly requests a copy of manuscripts intended for submission for publication least 60 days in advance of submission.

20 Revision History

Version Number	Date	Reason for Change
CIP 2.0	15 December 2017	Additional information about HRUC. Updates about incidences definitions. Updated starting date.
CIP 3.0	15 April 2019	Change in investigators. Updated enrolment period.
CIP 4.0	10 December 2019	Change in principal investigator at site Padova.

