8.4 End-points

Primary end-point

Change in overall health related quality of life via comparison of HUI3 multi-attribute utility scores at:

- **Post1** implant Visit compared to **Pre1** implant Visit
- **Post2** implant Visit compared to **Post1** implant Visit
- **Post2** implant Visit compared to **Pre1** implant Visit

Secondary end-points:

Change in scores on battery of evaluation tools for health related domains and overall well-being on each of the following:

MMSE, DSST & Trail B (Cognition); TUG (falls); GDS-15 (depression); iADL (independency); HHIE-S (hearing handicap); SSQ (hearing & communication ability); CAP-II (capabilities of audition); De Jong Loneliness Scale, Speech recognition tests in Quiet (daily hearing function); Speech recognition tests in Noise (daily hearing function); Consistent daily use of CI via automatic data logging (hrs/day and listening environments).

- **Post1** implant Visit compared to **Pre1** implant Visit
- **Post2** implant Visit compared to **Post1** implant Visit
- **Post2** implant Visit compared to **Pre1** implant Visit

Tertiary end point:

Changes in healthcare resource utilisation with CI treatment compared to preimplant, collected at each test interval, i.e., Pre 1, Post1 and Post 2 will be compared. Each assessment will reflect a 6 month period immediately before assessment. Data reviewed for this measure will be obtained from the customized HRU questionnaire completed by the clinician on behalf of the subject (data sources available for use will be in accordance with regional guidelines).

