8.6.3 Criteria and procedures for subject's withdrawal or discontinuation

Subjects can decide to withdraw from the investigation without indicating any reasons at any time. The patient will then continue to be managed by the clinic as per the routine clinical practice with the intention to treat the hearing impairment accordingly.

The investigator may decide to discontinue a patient due to major non-compliance with the Observational Study Protocol requirements (e.g. three-visit schedule not met) or in the event

the patient demonstrates rapid decline in overall health and is unable to participate in the study procedures.

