8.6.7 Number of subjects required to be included in the clinical investigation

The number of subjects to be enrolled will be **N=100** subjects across the seven investigator implant sites.

In view of possible attrition rate of 5 to 10 % of enrolled subjects, randomly lost to follow up during the course of the study any time after enrolment, all subjects enrolled will be included in the final analysis as the “intention to treat” cohort with the majority being assessed “as per protocol”.

The number of subjects recruited per site will reflect the local normal practices for treatment in the elderly population during the study enrolment time frame of 24 months. The study will aim to accrue subjects distributed across all study sites and languages to avoid site and cultural bias.

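### Section 17 instructs, and 8.6.3 permits, removal of subjects too unwell to take part, with no HUI3 collected at or after exit, so the losses are not random and the bias favours benefit

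*Protocol*

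**What the plan says.** - **Endpoint.** Protocol 8.4 defines the primary endpoint as "Change in overall health related quality of life via comparison of HUI3 multi-attribute utility scores at" the three pairs of visits. Under 8.5 each subject is their own control.
- **Instruction to remove.** Protocol section 17 applies to "general health decline during the course of the study, preventing their comfortable participation in the study processes". In that case "the clinician should react in a timely manner to remove the subject from the study formally by completion of the end of study form".
- **Permission to discontinue.** Protocol 8.6.3 begins "The investigator may decide to discontinue a patient due to major non-compliance with the Observational Study Protocol requirements" and adds, as an alternative ground, that "the patient demonstrates rapid decline in overall health and is unable to participate in the study procedures". This is discretionary, and inability to participate is part of the condition.
- **Assumed mechanism.** Protocol 8.6.7 refers to a "possible attrition rate of 5 to 10 % of enrolled subjects, randomly lost to follow up during the course of the study", and says that every enrolled subject enters the final analysis as an intention-to-treat cohort.
- **Analysis.** SAP 7.1 keeps all participants, rules out imputation, and states that its methods give estimates free of bias when values are missing. It attaches no condition to that statement. No sensitivity analysis for informative dropout is planned.

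No section of either document asks for a HUI3 at the time of removal or at the remaining scheduled visits.

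**The concern.** The event that ends observation is a deterioration in health, and health is what the primary endpoint measures. Subjects who leave for this reason would be expected to have less favourable HUI3 changes than those who stay. A subject removed before month 12 contributes a baseline and no observed change, so inclusion in the analysis cohort does not bring the missing outcome back.

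The study has one arm. In a controlled comparison, similar removal in both arms might partly cancel; here nothing offsets it, and the estimated gain moves upward. L-IADL, TUG, the cognitive tests and resource use are exposed in the same way.

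At stake are the size of the reported gain, the 12-to-18-month comparison and small secondary effects. The documents describe the losses as harmless, so a reader of the results would have no warning.

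**Working it through.** **1. The plan's own figures reproduce, and power is not the problem.** Inputs (SAP section 5): change 0.10, SD of change 0.25, 90% power, 5% level; two-sided paired t-test (Protocol section 9). Standardised change = 0.10/0.25 = 0.4. The noncentral t distribution gives n = 68 (power 0.902) at 0.05 and n = 88 (power 0.903) at 0.05/3, as stated. Losing 5 to 10% of 100 leaves 95 to 90 subjects. Power is then 97 to 96% at 0.05 and 93 to 91% at 0.05/3. The question is bias.

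**2. Bias of a completer mean.** Let d be the share removed, c the mean change in completers and m the mean change in those removed. The mean over everyone is (1 - d)c + dm, so the completer mean is too high by d(c - m).

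Inputs:
- d = 0.05 to 0.10 (Protocol 8.6.7), taking all attrition as decline-driven, which is an assumption;
- c = 0.10 (planning value) or 0.165 (mean in the earlier data set, Protocol section 9);
- m = -0.10 or -0.20, an assumption, since the documents give no figure.

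| c | m | d = 0.05 | d = 0.10 |
|---|---|---|---|
| 0.10 | -0.10 | 0.05 x 0.20 = 0.010 | 0.10 x 0.20 = 0.020 |
| 0.10 | -0.20 | 0.05 x 0.30 = 0.015 | 0.10 x 0.30 = 0.030 |
| 0.165 | -0.10 | 0.05 x 0.265 = 0.013 | 0.10 x 0.265 = 0.027 |
| 0.165 | -0.20 | 0.05 x 0.365 = 0.018 | 0.10 x 0.365 = 0.037 |

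Two of the eight results reach the minimum important change of 0.03 (Protocol 5.2.1 and section 9). The result is proportional to d: if half the attrition were decline-driven (assumption), the range would be 0.005 to 0.018.

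**3. Upper-end scenario.** If changes were normal with SD 0.25 and exactly the lowest 5% or 10% were lost, the completer mean would be too high by 0.027 or 0.049. This implies removed subjects averaging about 0.52 or 0.44 below the overall mean, so it serves as a bound and not as a forecast.

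**4. Does the SAP's mixed model remove the bias?** A mixed model is unbiased if missingness depends only on observed values. For a subject removed before month 12, the only observed HUI3 is the baseline, and the decline that triggered removal is not recorded. The scenario in step 3 was run through a categorical-visit model with unstructured covariance. The assumed baseline-to-follow-up correlation was 0.3 to 0.7.
- Removal before month 12: bias of about +0.02 to +0.04 at 12 months and +0.01 to +0.02 at 18 months.
- Removal between months 12 and 18: about +0.01 to +0.04 at 18 months and none at 12 months.

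In that scenario the model leaves part of the bias in place, so the unconditional claim in SAP 7.1 does not hold.

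**The case against.** The strongest reply is that a subject too ill to participate would be missing under any rule. The removal rule itself costs only those who could still answer the HUI3 but leave because of the wider battery, and the documents give no size for that group. This stands: better conduct recovers part of the loss, and a sensitivity analysis must cover the rest.

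Flexibility elsewhere also counts. Protocol section 12 asks for compliance only as far as possible, SAP section 4 lets clinics choose optional measures, and the separate Procedure document (8.7) was not available. But nothing in the two documents says that a subject who can manage only the HUI3 stays in the study. It also stands that data obtained before removal are kept, so someone removed after month 12 still contributes a 12-month change.

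A reader might go further than the text allows in five ways:

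- **That both sections order removal of anyone whose health declines.** Section 8.6.3 only permits it, and in both sections the decline must prevent participation. That narrows the group to the sickest.
- **That section 17 contradicts 16.2.** There, "Study follow up shall continue when appropriate and ethical"; the sentence is conditional and sits in a section on device incidents. A decline that prevents comfortable participation fits within the condition.
- **That safety follow-up is lost.** General health decline is not listed as a safety endpoint in 8.4, subjects who withdraw stay under routine clinic care (8.6.3), and incidents have their own reporting route in section 16.
- **That the missed-visit ground in 8.6.3 is part of the same problem.** It is a non-compliance ground and is not tied to health.
- **That the bias could overturn the primary result.** Even the bound of 0.049, taken from the lower limit of 0.109 in the earlier data set, leaves 0.060, which is above 0.03.

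**Conclusion.** The point holds. Exit under section 17, and where used under 8.6.3, is related to the primary outcome, and no HUI3 is requested at or after it. The description of losses as random in 8.6.7 and the unconditional claim in SAP 7.1 are therefore unsupported. The direction, towards benefit, follows from the single-arm design, provided that subjects removed for decline do worse on HUI3 than those retained.

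The size is uncertain. The figure of about 0.010 to 0.037 describes a completer mean, takes all 5 to 10% attrition as decline-driven, and uses assumed changes in those removed. It shrinks in proportion if other reasons account for part of the losses. That is enough to matter for the size of the gain and for small effects, but not to show that a gain like the earlier data set's would disappear.

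**What to change.** 1. **Protocol 8.6.3 and 17:** separate stopping burdensome study assessments from leaving the study. Where the subject agrees and is able, still collect HUI3 (10 to 15 minutes, with the assistance 8.7 already allows) and the clinician-completed L-IADL (file and interview, about 5 minutes) at 12 and 18 months, or at removal if that is not possible. This concerns data collection only and changes nothing in treatment.
2. **End-of-study form:** make sure that the reason and date of removal are recorded. The form was not available and may already do this.
3. **Protocol 8.6.7:** delete the word describing the losses as random.
4. **SAP 7.1:** replace the unconditional claim with a stated missing-at-random assumption.
5. **SAP:** add one delta-adjusted sensitivity analysis for HUI3, over a range of unfavourable changes in subjects removed for decline (for example -0.10 and -0.20), and state how deaths are handled. Protocol 5.2.1 implies that death lies at 0 on the scale, while section 9 describes 0 as poor health, so the choice should be explicit.

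The cost is some wording, one additional analysis and a few assisted HUI3 completions by subjects who are unwell, which is why agreement and ability must be conditions. The estimate may come out slightly less favourable. Items 3 to 5 alone would not recover data that were never collected.

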20.1 Changes from version 2.0 to version 3.0

Cover page: [REDACTED] is added as author.

Introductory table: Investigators are updated to reflect the change of PI at Bnai Zion Medical Center and inclusion of the new site Rabin Medical Center (Beilinson). The sentence on sponsor activities is removed.

Section 1: Principal Investigators and sites are updated accordingly. Enrolment period is extended from 24 to 31 months.

Section 8.1: “if not agreed differently” is added as a condition to the anticipated subject recruitment number.

Section 8.6.8: Enrolment period and number of clinics are updated accordingly.

Section 11: The reference to a template is removed as no longer used to document CIP changes.

Section 22 Appendix I: List of investigators is updated accordingly.

20.2 Changes from version 1.0 to version 2.0

Cover page: A note is added for “Observational” as this terminology tends to disappear from national classification. In France and in Spain, the study is classified as “low risk intervention” in regards to the additional assessments performed.

Introductory table: The details of the Clinical Research Organisation (CRO) is updated

CIP Signature page: Sponsor signature, the name and function are updated

Section 1: Starting date is updated in the Clinical Investigation Synopsis to the real starting date: 06 November 2017

Section 5.2.10: HRCU paragraph has been updated to answer Ethical committee request to provide additional details. The time to complete the assessment has been updated.

Section 9: For clarity additional text was added in regards to Intra endpoint comparison. As well, it was added that statistical analysis plan is available as separate document.

Section 16: Definition of incidents has been updated to reflect changes in the MDR regulation

Section 19: A potential preliminary publication for completion of 1 year evaluation by a subgroup of the study cohort has been added.

21 Bibliography

de Jong Gierveld, J., & van Tilburg, T.G. (2006). A 6-item scale for overall, emotional, and social loneliness: Confirmatory tests on survey data. *Research on Aging*, 28, 582-598

http://home.fsw.vu.nl/tg.van.tilburg/manual_loneliness_scale_1999.html

De Raeve L, and van hardeveld R, Prevalence of cochlear implants in Europe: what do we know and what can we expect? *Journal of Hearing Science*, 2013, Vol 3, 9-16

Statistical Analysis Plan for the Cochlear Implant and Healthy Ageing Observational Study- CEL5671

Commercial in Confidence

Version 1.0

**Prepared for Cochlear Limited
21st January, 2018**

[figure not shown]

Table of Contents

| | |
|------------------------------------|----|
| Glossary..... | 3 |
| 1. Source documents | 3 |
| 2. Overview of the protocol | 3 |
| 3. Objectives of the Study | 4 |
| 4. Study Design..... | 5 |
| 5. Sample size..... | 5 |
| 6. Study outcomes | 5 |
| 7. Statistical Analysis Plan | 11 |
| 5. Data Handling..... | 11 |
| 6. Statistical Methods | 11 |
| References | 14 |

CI & HEALTHY AGEING OBSERVATIONAL STUDY - STATISTICAL ANALYSIS PLAN

Glossary

| | |
|---------|--|
| CI | Cochlear Implant |
| CAP-II | Capabilities of Auditory Performance test |
| DSST | Digit Symbol Substitution Test |
| GDS-15 | Geriatric Depression Scale-15 |
| HHIE-S | Hearing Handicap Inventory for the Elderly Scale |
| HUI 3 | Health Utility Index (HUI) Mark (version) III |
| L-iADL | Lawton-instrumental Activities of Daily Living |
| MMSE | Mini Mental State Examination |
| PTA | Pure Tone Audiometry |
| SFT | Sound Field Thresholds |
| SSQ | Speech Spatial and Qualities questionnaire |
| Trail B | Trail Making Test Version B |
| TUG | Timed Up and Go test |

1. Source documents

This Statistical Analysis Plan (SAP) is based on

- i. The Cochlear® document observational study protocol document entitled: **Cochlear Implant and Healthy Aging: A Multinational, Multicentre Observational Study** written by [REDACTED]
- ii. The sample case report forms

2. Overview of the protocol

With an ageing population comes an increasing burden of disease and a high associated economic cost. Among the leading contributors to burden of disease in people over 60 are sensory, mental and neurological disorders as well as unintentional injury with hearing loss considered one of the 15 most burdensome disorders (Prince et al, 2015).

Cochlear Implant (CI) treatment restores hearing function which enables communication. The ability to communicate reduces the potential for social isolation. This study aims to show that CI treatment improves overall health related quality of life and general well-being in CI candidates aged 60 or older with bilateral post-lingual deafness.

Using a series of standardised forms and a variety of questionnaires, participants will have data gathered pre-implant and then at 12 and 18 months post-implant.

The aim, as described in the protocol, is to provide transparent and comparable medical evidence that can support health care policy makers to take informed decisions on the provision of health services for the treatment of hearing loss. A brief summary of the protocol follows.

3. Objectives of the Study

The primary objective is to evaluate the change in health-related quality of life following CI treatment by using the generic Health Utilities Index Mark III (HUI 3) multi-attribute index score. All pairwise comparisons are of interest i.e. preimplant to 12 months postimplant, preimplant to 18 months postimplant, and the change from 12 to 18 months.

A secondary objective involves evaluating the impact of CI treatment in the elderly on domains that may be associated with healthy aging and overall well-being such as

- hearing ability (using the Capabilities of Auditory Performance (CAP-II) test, the Speech Spatial and Qualities (SSQ) questionnaire, the Hearing Handicap Inventory for the Elderly Scale (HHIE-S), speech recognition tests in the quiet and in noise, pure tone audiometry (PTA) and sound field thresholds (SFT))
- independence (using the Lawton-instrumental Activities of Daily Living (L-iADL) tool)
- cognition (using the Mini Mental State Examination (MMSE) score, the Digit Symbol Substitution (DSST) test and the Trail Making Test version B (Trail B))
- falls (using the Timed Up and Go test (TUG))
- depression (using the Geriatric Depression Scale-15 (GDS-15), and the De Jong Loneliness Scale)
- CI usage measures.

All pairwise comparisons between time points, as defined above, are of interest here also.

A tertiary objective is to identify healthcare resource utilisation that is impacted by comparing costs post CI treatment with those prior to treatment.

For all of these objectives, interest is also in whether various demographic variables are associated with the change in outcome scores observed.

In summary:

Primary hypothesis

CI treatment significantly improves the overall health related quality of life of elderly individuals compared to their pre-implant condition (and again from 12 to 18 months following surgery) as measured by the HUI3 multi-attribute score.

Secondary hypothesis

CI treatment significantly impacts healthy aging domains and wellbeing of elderly individuals compared to their pre-implant condition (and again from 12 to 18 months following surgery) as measured by clinically standard evaluation tools in the geriatric and audiological fields (as described above)

Tertiary hypothesis

CI treatment significantly reduces healthcare resource utilisation in elderly individuals over time.

Other hypotheses

There are covariates associated with the change in health-related quality of life and other healthy aging domains and related well-being.

4. Study Design

The study is a prospective observational longitudinal study performed to evaluate the benefits for overall health following CI treatment in the elderly population treated in routine clinical practice. Multiple centres are included in the study

Implantation with commercially available cochlear implant devices (i.e. products approved for market release) available for routine clinical treatment of deafness in all ages in collaborating investigator clinic sites is made as part of the study and no additional interventions are applied.

Change in outcome scores for various standard assessment tools and health domains post CI treatment compared to the pre-implant status are made using participants as their own controls. All questionnaires of interest are administered at each visit (up to 2 months pre-implant, 12 months post-implant [+/- 1 month] and 18 months post-implant [+/- 1 month]).

Whilst a recommended evaluation schedule is provided, participating clinics may select the optional evaluation measures they wish to use for their patients from the tools made available on the study specific electronic platform at baseline registration of each patient.

Participating in the study is voluntary and the participant is free to electively cease participation in the registry at any time. To be included in the study, participants must meet all local and study specific inclusion criteria and have none of the exclusion criteria. Participants remain in the study for a period of up to 2 years.

5. Sample size

Assuming that a paired t-test of the change in HUI3 multi attribute score from pre-implant to 12 or pre-implant to 18 months following implantation is of interest, then with 90% power and a 5% level of significance a change of 0.1 with standard deviation of change equal to 0.25, would require 68 participants.

Because all pairwise tests are of interest one method for undertaking this is to perform multiple tests and then adjust the significance level for the number of comparisons (in this case 3). This is equivalent to having a significance level of $0.05/3 = 0.0167$ and is a form of Bonferroni correction. If we recompute the sample size required with this significance level then at least 88 participants would be needed to find a change of 0.1 units in the HUI3 significant.

6. Study outcomes

The outcomes measures described in section 3 are detailed in the Protocol document and are briefly described here. This section could be updated when a better understanding of the distribution of the outcome measures is obtained through the data collected.

HUI 3

The HUI3 is a 15-item questionnaire. Responses to items are converted to levels and a scoring function applied. The ultimate result is a series of domain scores and a multi-attribute score. Domain scores typically don't have continuous distributions and need to be analysed with care. The multi-attribute score may be treated as continuous and is the focus of this study. Higher scores indicate less impairment.

CAP-II

The CAP-II comprises 9 questions placing each participant into one of 10 ordinal categories that determines their auditory performance at the time of assessment. Scores range from 0 (no awareness of environmental sounds or voice) through to 9 (use of telephone with unknown speaker in unpredictable context) so that higher scores imply better performance. These scores are an ordinal categorical scale and should not be treated as continuous.

SSQ

The SSQ is a 49-item questionnaire utilising a 10-point numerical rating scale for each question. The SSQ comprises three main subscales; speech perception (using the first 14 questions), spatial hearing (using the next 17 questions) and other qualities of hearing (using the last 18 questions).

Each subscale is the average of the scores from each subscale item; so, for example, scores on the speech component are between 0 and 10. These scores may be assumed to be continuous, higher scores imply better performance.

HHIE-S

The HHIE-S is a 10-item short form that assesses the impact of hearing impairment on emotional and social adjustment. Higher scores indicate greater handicap. The distribution is described as continuous.

Speech recognition in quiet

This tool measures the percentage of items correctly identified at 65dB SPL or the speech perception threshold level (dB SPL) at which 50% of speech items can be correctly recognised. The distribution of the first outcome may be binomial while the second is likely continuous. These outcomes need to be explored in more detail when data are available.

Speech recognition in noise

This tool measures the percentage of items correctly identified at 65dB SPL with noise in the background or the speech perception threshold level (dB SPL) at which 50% of speech items can be correctly recognised with noise in the background. The distribution of the first outcome may be binomial while the second is likely continuous. These outcomes need to be explored in more detail when data are available.

PTA

Pure tone audiometry are the unaided hearing thresholds for pure-tone stimuli via air conduction. Various frequencies will be examined. For analysis purposes, these outcomes will be presented as a descriptive mean group threshold per interval.

SFT

Sound field thresholds are the aided hearing thresholds for warble-tone stimuli presented in the sound field. Various frequencies will be examined. For analysis purposes, these outcomes will be presented as a descriptive mean group threshold per interval.

TUG

The timed up and go (TUG) test measures the time a person takes to stand up from a chair, walk three metres, turn around, walk back to the chair and sit down again. This is a continuous measure.

GDS-15

The Geriatric Depression Scale -15 (GDS-15) is a 15-question self-report. A 1 is assigned to the “negative” (i.e. more depressive) responses to each item and a 0 to the “positive” responses. The sum of the items is taken. This is likely to be able to be treated either as a continuous or a binomial response though the responses will need to be explored further to determine the distribution.

MMSE

The mini-mental state examination is a 30 point cognitive screening test resulting in scores between 0 and 30. The distribution is typically skewed to the left with most scores being close to the boundary of 30 in a cognitively healthy population. The protocol notes that analysis will need to adjust for age, gender and education level as these variables impact the MMSE score.

DSST

The digit symbol substitution test is a working memory test that is used as an indicator of brain damage, dementia and depression. The number of correct responses in a given time span is collected. This is likely to be able to be treated as a continuous response though the distribution of responses should be examined carefully.

Trail B

The Trail B test is a cognitive test that assesses executive function. The time taken to correctly complete a “trail” of letters and numbers is recorded up to a maximum of 5 minutes. This is a continuous response that is likely to be normally distributed in a healthy population. The distribution should be examined before analysis in the sample explored in this study.

L-iADL

The Lawton Instrumental Activities of Daily Living scale gauges level of disease and a patients' ability to look after him or herself. Activities assessed require mental and physical capacity and determine what a person could rather than does do. Scores on 8 items (given either a 1 or 0) are summed to give a total score, higher scores indicate more independence. This may be able to be treated as a continuous response though the distribution of responses should be examined carefully prior to analysis.

De Jong Loneliness

The De Jong Loneliness scale is a 6-item questionnaire. Each question has 3 possible responses one of which is negatively worded and the others considered positive or neutrally worded. Neutral and positive responses are scored a 1 on the negatively worded items and neutral and negative responses are scored a 1 on the positively worded items. A sum of the responses is obtained giving a range of scores from 0 to 6 in which higher scores indicate greater loneliness. This may be able to be treated as a continuous response though the distribution of responses should be examined carefully prior to analysis.

CI Usage

Daily usage data are logged in the implanted device and will be recorded at post-implant assessments.

Patient Profile Data

A variety of patient demographics will be collected. The table below describes some of these variables and the classification (as categorical or otherwise) of these variables.

Table 1: Patient Profile Data

| Question number | Variable | Classification |
|-----------------|--|---|
| 1.1 | Native language | Categorical (nominal) |
| 1.2 | Other languages | Categorical (nominal) |
| 1.3 | Local town/ city population | Categorical (ordinal) |
| 1.4 | Household description | Categorical (nominal) |
| 1.5 | People in household Age Dependent? | Continuous Categorical (binary) |
| 1.6 | Education level | Categorical (ordinal) |
| 1.7 | Work status | Categorical (nominal) |
| 1.8 | Work level | Categorical (ordinal) |
| 1.9 | Job title | NA |
| 1.10 | Job classification | Categorical (nominal) |
| 2.1 | Weight (kg) | Continuous |
| 2.2 | Height (cm) | Continuous |
| 3.1 | How often smoking? | Categorical (ordinal) |
| 3.2 | Smoking level | Discrete (counts) |
| 3.3 | Ever smoked? | Categorical (binary) |
| 3.4 | Years regular smoking | Continuous |
| 4.1 | Alcohol how often? | Categorical (nominal, because of refusal) |
| 4.2 | Frequency of more than 6 drinks | Categorical (nominal, because of refusal) |
| 5.1 | Tinnitus frequency | Categorical (nominal, because of DK) |
| 5.2 | Does tinnitus affect activities? | Categorical (nominal, because of DK) |
| 5.3 | Does tinnitus affect sleep | Categorical (nominal, because of DK) |
| 6.1 | Exercise level | Categorical (ordinal) |
| 6.2 | Exercise undertaken | Categorical (nominal) |
| 6.3 | Hours of gentle exercise | Categorical (ordinal) |
| 6.4 | Hours of moderate exercise | Categorical (ordinal) |
| 6.5 | Hours of vigorous exercise | Categorical (ordinal) |

HRU Data

Healthcare resource utilisation data will be collected. The variables in this data set

Table 2: Health resource utilisation data

| Question number | Variable | Classification |
|-----------------|--|--|
| CSL1 | Several yes/no questions about insurance modalities | Categorical (binary) |
| CSL2 | Cost of voluntary private insurance per month | Continuous |
| CSL3 | Cost of employer provided insurance per month | Continuous |
| CSL4 | Percentage of various insurance options covered | Continuous |
| CSL5a | Employment status 6 months ago | Categorical (nominal) |
| CSL5b | Employment status 6 months ago | Categorical (nominal) |
| AP1 | Number of visits to various primary care or emergency care centres Number of visits Number of visits due to ears | Discrete Discrete |
| AP2 | How to travel to centre? Primary care Emergency | Categorical (nominal) Categorical (nominal) |
| AP3 | How long to travel to centre by foot? Primary care Emergency | Categorical (ordinal) Categorical (ordinal) |
| AP4 | Cost of travel to primary care | Continuous |
| AP5 | Primary care out of pocket cost | Continuous |

| | | |
|------|--|---|
| AP6 | Emergency care out of pocket cost | Continuous |
| AP7 | Who accompanies you? Primary care Emergency | Categorical (nominal) Categorical (nominal) |
| ES1 | Number of visits to specialists Type of specialist Number of visits | Categorical (nominal) Discrete |
| ES2 | Number of outpatient or day procedures Type of procedure Number of occurrences | Categorical (nominal) Discrete |
| ES3 | How to travel to specialist/outpatient centre? | Categorical (nominal) |
| ES4 | How long to travel to centre by foot? | Categorical (ordinal) |
| ES5 | Cost of travel to specialist/outpatient centre | Continuous |
| ES6 | Specialist/outpatient centre out of pocket cost | Continuous |
| ES7 | Who accompanies you to specialist/outpatient centre | Categorical (nominal) |
| PD1 | What type of functional/special tests (by test) Number of tests Number of tests due to ears Out of pocket cost of tests | Categorical (nominal) Discrete Discrete Continuous |
| | What type of radiology (separately by test) Number of tests Number of tests due to ears Out of pocket cost of tests | Categorical (nominal) Discrete Discrete Continuous |
| | What type of laboratory tests (separately by test) Number of tests Number of tests due to ears Out of pocket cost of tests | Categorical (nominal) Discrete Discrete Continuous |
| | In hospital tests in last 6 months Admission and discharge dates DRG code Hired person accompanying? Family accompanying? | Dates ¹ Categorical (nominal) Categorical (nominal) Categorical (nominal) |
| | Out of pocket costs for hospitalization in last 6 months Not related to hearing Related to hearing | Continuous Continuous |
| | Prescription medications taken (per type) Start and end date Daily dose Proportion out of pocket Cost per month Related to hearing? | Categorical (Nominal) Dates ² Continuous Continuous Continuous Categorical (binary) |
| | Non-prescription medications taken (per type) Start and end date Daily dose Proportion out of pocket Cost per month Related to hearing? | Categorical (Nominal) Dates ² Continuous Continuous Continuous Categorical (binary) |
| PHT1 | Received physiotherapy/rehab in last 6 months | Categorical (binary) |
| PHT2 | How many weeks of physio/rehab? | Discrete |
| PHT3 | Days per week of physio/rehab? | Discrete |
| PHT4 | Hours per day of physio/rehab? | Continuous |
| PHT5 | Percentage of sessions due to ear-related problems | Continuous |
| PHT6 | Had out of pocket costs for physio/rehab? | Categorical (binary) |
| PHT7 | How much out of pocket per month? | Continuous |
